5.7.4.3 Sensitivity Analysis

No sensitivity analysis will be performed.

5.7.4.4 Subgroup Analysis

No subgroup analyses will be performed.

5.7.5 Randomised double-blind period: Analysis of Other Secondary Efficacy Endpoints

5.7.5.1 Endpoint, Treatment Effect and Estimand Definition

To assess the exploratory objectives, the treatment policy estimand is defined by the following key attributes:

- Population: Subjects in the randomized population
- Assessments: Described in table below
- Variables (Endpoints): Described in table below

- Intercurrent event: None
- Population-level summary (estimate of the treatment effect): Described in table below

Assessment	Variables (Endpoints)	Population-level summary (estimate of the treatment effect)
QoL assessed by the SF-36 questionnaire	Change from baseline in SF-36 scores at each scheduled timepoint	Difference between each Dysport doses and the placebo group in the SF-36 scores at each scheduled timepoint
Use of rescue medication during the study	Amount of rescue medication taken during the study	Difference between each Dysport doses and the placebo group, in amount of rescue medication intake during Part B
Use of rescue medication during the study	Time to first intake of rescue medication in days Derivation: Difference in days between date of the first intake of rescue medication and date of IMP administration.	Difference between each Dysport doses and the placebo group, in the time to first intake of rescue medication during Part B

Quality of life

QoL is assessed at day -1, week 6 and week 12 by the SF-36 questionnaire. The SF-36 consists of 36 questions divided in 9 scaled scores: General health, Reported health transition, Physical functioning, Role physical, Role emotional, Social functioning, Bodily pain, Vitality, Mental health. For more details about the derivation of the scores, see section 7. Two versions of the questionnaire were used in the study, mapping was performed to homogenize the answers, see section 7 for details about mapping rules.

In addition, a global score per patient will be derived as the sum of the individual scores at each question. It will range from 0 to 3600.

Rescue Medication

Rescue medications will be coded using the latest version of WHO-DD in effect within IPSEN at the time of database lock.

The total amount of rescue medication will be derived.

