2.6 Change from Statistical Section of the Protocol

The following endpoints were not planned in the statistical section of the Protocol but were added in section 5.7.4.1 (Efficacy parameters) and 5.7.5.1 (Rescue medication): SPID and AUE. The reason for this change is to have additional information for the description of the pain response. Date of agreement of change is 03MAY2019.

The sensitivity analyses originally planned in the protocol in section 11.3.3.2 to take into account the intake of rescue medication and to handle missing data will not be

performed due to the low number of rescue medication taken and the difficulty to associate the NRS score assessment to the rescue medication. This will be confirmed during the blind data review meeting, before the database lock. Date of agreement of change is 04JUN2019.

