All raw and derived variables will be listed and described using summary statistics. For categorical variables, summary statistics will be displayed using descriptive statistics by frequency count and percentages by category. The missing category will be presented if there is one missing category for at least one treatment group. Except otherwise specified, subjects with missing data will not be included in the calculation of percentages. For quantitative variables, summary statistics will be displayed using descriptive statistics by number of observations, mean, standard deviation (SD), first quartile, median, third quartile, minimum and maximum. Missing data will be displayed.

5.1.3 *Baseline value*

Unless otherwise specified, baseline is defined as the last non-missing measurement taken within 7 days prior to IMP administration (including unscheduled assessments).

For the spontaneous NRS score, baseline will be defined as the mean of all pre-dose data (from day -7 and including pre-dose on Day 1).

5.1.4 *Reference Start Date and Study Day*

Reference start date is defined as the day of IMP administration in Part B.

The day of IMP administration will be Day 1. Study day will be calculated as:

- The difference between the event date and the reference date plus one day, if the event is on or after the reference date.
- The difference between the event date and the reference date, if the date of event is prior to the reference date.

Study day will appear in any Part B listings where an assessment date or event date appears.

In case of partial or missing event date, study day will appear missing while any associated durations will be presented based on the imputations described in appendix A3.

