5.7.1.2 Statistical/analytical issues

Adjustments for Covariates

Not applicable

Handling of Dropouts or Missing Data

The strategy for missing data handling is specified in each relevant section.

Interim Analyses and Data Monitoring

Please refer to section 3.

Multicentre Studies

Not applicable

Multiple Comparisons/Multiplicity

No formal statistical significance testing will be performed.

Use of an "Efficacy Subset" of Subjects

Not applicable

Active-Control Studies Intended to Show Equivalence (if applicable)

Not applicable

Examination of Subgroups

Subgroups analyses will be detailed in the concerned sections.

5.7.2 *Pre-randomisation run-in period*

A listing presenting NRS data will be provided. The listing will present, by subject, the planned visit and timepoint, the treatment administered, the assessment dates and the NRS scores.

5.7.3 *Randomised double-blind period: Analysis of Primary Efficacy Endpoint*

5.7.3.1 *Endpoint, Treatment Effect and Estimand Definition*

To assess the primary objective, the treatment policy estimand is defined by the following key attributes:

- Population: Subjects in the randomized population
- Assessment: Worst pain and average pain within the last 12 hours as assessed by the spontaneous NRS score
- Variables (Endpoints): Described in table below
- Population-level summary (estimate of the treatment effect): Described in table below

Variables (Endpoints)	Population-level summary (estimate of the treatment effect)
Time to onset i.e. time to decrease from baseline of two points in the spontaneous NRS score. Derivation: First scheduled time point for which the change from baseline is ≤ -2 points.	The number (%) of subjects who reach the time to onset in each treatment group. The mean time to onset in each treatment group
Peak effect i.e. maximal decrease from baseline in the spontaneous NRS score. Derivation: Minimum change from baseline amongst the scheduled timepoints	The mean peak in each treatment group
Time to peak-effect i.e. time to reach the peak-effect Derivation: First timepoint for which the peak effect is reached	The mean time to reach the peak-effect in each treatment group

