5.7.5.2 Analysis

Quality of Life

A listing of individual responses to the SF-36 questionnaire will be prepared.

For each question of the SF-36 questionnaire, a summary table presenting the raw scores and change from baseline will be generated by dimension, treatment group and measurement time.

Arithmetic means of the global scores will be presented on a histogram by treatment group, with all visits and dimensions on the same graph. Arithmetic means of the

global scores will also be presented on a histogram by dimension, with all visits and treatment group on the same graph.

Individual histograms presenting mean scores by dimension and visit will be produced, with all dimensions on the same graph.

Rescue Medications

A listing of rescue medications will be provided, including the total amount of rescue medication and the time from D1 to first intake of rescue medication.

Summary of count and percentages of subjects having at least one rescue medication will be provided by ATC class and preferred Name, by treatment group.

Summaries of the total amount of rescue medication by preferred Name and the time to first intake (in days) will be provided by treatment group and Placebo group versus all Dysport groups. The number of subjects using a rescue medication and the number of rescue medication taken will also be described by treatment group.

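### Time to first rescue has no rule for subjects who take no rescue, so as derived the planned Dysport–placebo difference compares users only

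*SAP*

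**What the plan says.** Time to first intake is one of two rescue-medication endpoints serving a named exploratory objective (SAP 2.1, 5.7.5.1).

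- **Derivation (SAP 5.7.5.1):** "Difference in days between date of the first intake of rescue medication and date of IMP administration".
- **Treatment effect (same table):** "Difference between each Dysport doses and the placebo group, in the time to first intake of rescue medication during Part B". Protocol Table 5 names the same endpoint and difference.
- **Estimand attributes (same section):** "Population: Subjects in the randomized population" and "Intercurrent event: None".
- **Output (SAP 5.7.5.2):** "the time to first intake (in days) will be provided by treatment group and Placebo group versus all Dysport groups". The same section plans user counts and percentages by arm and a listing that includes each subject's time to first intake.
- **Statistics for a quantitative variable (SAP 5.1.2):** "descriptive statistics by number of observations, mean, standard deviation (SD), first quartile, median, third quartile, minimum and maximum". Missing data are to be displayed.
- **Missing data (SAP 5.7.1.2):** "The strategy for missing data handling is specified in each relevant section". SAP 5.7.5 contains no such strategy for rescue medication, and Protocol Table 5 adds none.
- **Expected use (SAP 2.6):** the sensitivity analyses for rescue intake and missing data are dropped, partly "due to the low number of rescue medication taken", subject to confirmation at the blind data review.

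**The concern.** Going the whole 16 weeks without rescue is the best possible result on this endpoint, yet it yields no number under the stated derivation. Someone who leaves in week 3 without having taken rescue also yields no number, and the plan does not separate that case from 16 rescue-free weeks. What remains to be summarised is the timing of intake among those who took rescue. That group is formed after randomisation and may itself depend on treatment.

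The declared estimand and the computable quantity therefore differ. One refers to all randomised subjects, the other to users. If Dysport works mainly by preventing any need for rescue, that benefit is absent from the time comparison, and one early user in an otherwise rescue-free arm can set that arm's mean. An arm with no users has no mean, so its difference from placebo does not exist.

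**Working it through.** **1. Who has a value under the rules as written**

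| Subject's course after dosing | First-intake date | Value from SAP 5.7.5.1 | Information actually available |
|---|---|---|---|
| Takes rescue | yes | days from dosing | event time |
| Completes 16 weeks, no rescue | no | none | event-free to end of study |
| Withdraws before any rescue | no | none | event-free to last contact |

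Only the first row enters the mean, quartiles and between-arm difference.

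**2. Inputs**

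- Arm size, from SAP 2.3 and the 3:1:3:1:3:1 ratio in SAP 2.4.2: 24 × 3/12 = 6 per Dysport dose and 24 × (1+1+1)/12 = 6 for pooled placebo. This reproduces the plan's 24 as 4 × 6.
- Follow-up, from Protocol 3.3: 16 weeks × 7 = 112 days.
- Rescue rates and intake days: not given in the documents. Everything assumed below is illustrative.

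**3. An assumed, deliberately extreme data set**

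Placebo: 5 of 6 take rescue, on days 10, 20, 40, 60 and 80. One Dysport arm: 1 of 6, on day 5. Nobody leaves early.

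- Users-only means: placebo (10+20+40+60+80)/5 = 42.0 days; Dysport 5.0 days. Difference 5.0 − 42.0 = −37.0 days, so Dysport appears to need rescue sooner.
- Restricted means, with non-users event-free to day 112: placebo (210+112)/6 = 53.7 days; Dysport (5 + 5×112)/6 = 94.2 days. Difference +40.5 days, so Dysport needs it later.
- Kaplan-Meier median: placebo 40 days; Dysport not reached.

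This shows only that the sign can change.

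**4. Expected values under a constant hazard**

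Let p be the 16-week probability of any rescue, F = 112 and λ = −ln(1−p)/F.

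- Users-only mean = 1/λ − F(1−p)/p
- Restricted mean to day F = p/λ

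| p placebo / Dysport | Users-only means (days) | Gap | Restricted means (days) | Gap |
|---|---|---|---|---|
| 0.83 / 0.17 | 40.3 / 54.3 | 14.0 | 52.5 / 102.2 | 49.7 |
| 0.67 / 0.17 | 45.9 / 54.3 | 8.4 | 67.7 / 102.2 | 34.5 |
| 0.50 / 0.17 | 49.6 / 54.3 | 4.7 | 80.8 / 102.2 | 21.4 |
| 0.33 / 0.17 | 52.3 / 54.3 | 2.0 | 92.3 / 102.2 | 9.9 |

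On average the users-only gap has the right sign but is only about 20 to 30% of the restricted-mean gap (for example 14.0/49.7 = 28% and 2.0/9.9 = 20%).

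**5. Behaviour in a single trial with 6 per arm**

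Simulation under the same hazards, 400,000 replicates. Percentages are of trials in which both arms have at least one user.

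| p placebo / Dysport | Users-only mean puts the low-rescue arm sooner | Restricted mean does so |
|---|---|---|
| 0.83 / 0.17 | 34.8% | 1.0% |
| 0.67 / 0.17 | 40.9% | 5.9% |
| 0.50 / 0.17 | 45.2% | 17.0% |
| 0.33 / 0.17 | 48.0% | 33.1% |

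The chance that an arm at p = 0.17 has no user is 0.83^6 = 0.327. In about a third of trials the planned difference for that arm cannot be calculated.

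**The case against.** Four points can be made for the plan.

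- **The SAP nowhere states that only users are averaged.** Where it wants a conditional mean it says so, as for duration of effect in SAP 5.7.3.1, and the table shells are a separate document. This stands as a matter of wording: restriction to users is a consequence of the derivation, not a declared intention. It does not supply the missing rule.
- **The planned outputs already expose the problem.** User counts and percentages by arm, the number of observations behind each mean and the individual listing would show, in the assumed data set, 5 of 6 users against 1 of 6. This also stands, and it lowers the risk of a misreading. The counts do not change what the stated difference in days compares.
- **The alternative is imprecise too.** In the lowest-use scenario the restricted mean has the wrong sign in 33.1% of trials. That is true with six per arm; it still does better than the users-only mean in every scenario examined.
- **Little hangs on the endpoint.** It is exploratory and descriptive, no test is planned, and the primary pharmacodynamic profile does not use it. This limits the weight of the point.

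A reader might also infer from SAP 2.6 that most subjects would drop out of the summary. The text does not support that. It speaks of little rescue medication being taken, not of how many subjects took none, and leaves even that to be confirmed at blind review.

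**Conclusion.** The gap is real and modest in consequence. Followed as written, the SAP gives no value to subjects without rescue, so its Dysport–placebo difference in time to first intake does not describe the randomised population it names. Under the assumed constant hazards, the expected gap falls to about 20 to 30% of the restricted-mean gap. The observed sign is wrong in 34.8% to 48.0% of trials with users in both arms. The difference is undefined in about 33% of trials for an arm with a rescue probability of 0.17.

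These figures rest on assumed rescue probabilities, constant hazards, six subjects per arm and no early withdrawal. The documents provide none of the rescue rates.

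A reader might conclude that the planned analysis will make an effective dose look worse. That goes too far: the expected direction is still right in every scenario above, and reversal is a possibility at this sample size rather than the typical result.

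**What to change.** Amend SAP 5.7.5.1 and 5.7.5.2 as follows.

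1. Define time to first rescue as a time-to-event variable in randomised and dosed subjects, with the dosing date as time zero. A randomised subject who was never dosed has no origin for the derivation.
2. Censor subjects without rescue at the end-of-study visit or, if withdrawn, at last contact.
3. Report by arm, and for placebo against all Dysport, Kaplan-Meier estimates and the restricted mean time to first rescue to Week 16, beside the user counts already planned. State the horizon in advance: the final visit may fall three days early (112 − 3 = day 109).
4. Label any mean among users as conditional on use, and state that it is not computed for an arm without users.

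No new data are needed. Dosing dates, rescue-diary dates (Protocol 10.2) and the last visit attended (SAP 5.8.2) are already collected. The cost is a paragraph of SAP text and minor extra programming with a standard procedure. Estimates will remain imprecise with six per arm. Censoring at withdrawal also assumes that leaving is unrelated to the coming need for rescue, so withdrawals before any rescue should be listed with their reasons.

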7 DERIVED DATA

QST data – Tactile detection thresholds

During the tactile detection test, the force (in g) recorded is in a logarithmic scale. To analyse the data, the values will be converted on a linear scale following the table below.

Filament	A	B	C	D	E	F	G	H	I	J	K	L	M	N	O	P	Q	R	S	T
Force (g)	0.008	0.02	0.04	0.07	0.16	0.4	0.6	1	1.4	2	4	6	8	10	15	26	60	100	180	300
Conversion	1	2	3	4	5	6	7	8	9	10	11	12	13	14	15	16	17	18	19	20

SF-36 Questionnaire – Score derivation

The SF-36 consists of 36 questions divided in 8 dimensions: General health, Physical functioning, Role physical, Role emotional, Social functioning, Bodily pain, Vitality, Mental health and one additional question on Reported health transition.

In each dimension, each question will be coded from 0 to 100, using the table below.

Question number	Original response	Analysis Value
1, 2, 6, 8, 11b, 11d	First modality: Excellent / Much better now than one year ago / Not at All / Definitely true	100
	Second modality: Very good / Somewhat better now than one year ago / Slightly / A little bit / Mostly true	75
	Third modality: Good / About the same / Moderately / Don't know	50
	Fourth modality: Fair / Somewhat worse than one year ago / Quite a bit / Mostly false	25
	Fifth modality: Poor / Much worse now than one year ago / Extremely / Definitely false	0
3a, 3b, 3c, 3d, 3e, 3f, 3g, 3h, 3i, 3j	First modality: Yes, Limited a Lot	0
	Second Modality: Yes, Limited a little	50
	Third modality: No, Not Limited at All	100
4a, 4b, 4c, 4d, 5a, 5b, 5c	First modality: Yes	0
	Second modality: No	100
7, 9a, 9d, 9e, 9h	First modality: None / All of the time	100
	Second modality: Very mild / Most of the time	80
	Third modality: Mild / A good bit of the time	60
	Fourth modality: Moderate / Some of the time	40
	Fifth modality: Severe / A little of the time	20
	Sixth modality: Very severe / None of the time	0
9b, 9c, 9f, 9g, 9i	First modality: All of the time	0
	Second modality: Most of the time	20
	Third modality: A good bit of the time	40
	Fourth modality: Some of the time	60
	Fifth modality: A little of the time	80
	Sixth modality: None of the time	100
10, 11a, 11c	First modality: All of the time / Definitely true	0
	Second modality: Most of the time / Mostly true	25
	Third modality: Some of the time / Don't know	50
	Fourth modality: A little of the time / Mostly false	75
	Fifth modality: None of the time / Definitely false	100

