Within each dimension, scores will be derived as the mean of the responses, thus scores will range from 0 to 100, with higher score defining a more favourable health. Missing data will not be taken into account and will not be replaced. Table below presents the number of questions by dimension.

Area	Dimension	Numbers of questions
Functional status	Physical functioning	10
	Social functioning	2
	Role physical	4
	Role Emotional	3
Wellbeing	Mental health	5
	Vitality	4
	Bodily pain	2
Overall evaluation of health	General Health	5
	Reported health transition	1
TOTAL		36

SF-36 Questionnaire – Mapping rules between Version 2.0 and 1.0

Question	Version 2	Version 1	Mapping rules
During the past 4 weeks, have you had any of the following problems with your work or other regular daily activities as a result of your physical health?	Modalities used are the following: - All of the time - Most of the time - Some of the time - A little of the time - None of the time	Modalities used are the following: - Yes - No	Modalities from version 1 will be mapped as follow: - All of the time => Yes - Most of the time => Yes - Some of the time => Yes - A little of the time => Yes - None of the time => No
During the past 4 weeks, have you had any of the following problems with your work or other regular daily activities as a result of any emotional problems (such as feeling depressed or anxious)?	Modalities used are the following: - All of the time - Most of the time - Some of the time - A little of the time - None of the time	Modalities used are the following: - Yes - No	Modalities from version 1 will be mapped as follow: - All of the time => Yes - Most of the time => Yes - Some of the time => Yes - A little of the time => Yes - None of the time => No
These questions are about how you feel and how things have been with you during the past 4 weeks. For each question, please give the one answer that comes closest to the way you have been feeling.	Modalities used are the following: - All of the time - Most of the time - Some of the time - A little of the time - None of the time	Modalities used are the following: - All of the time - Most of the time - A good bit of the time - Some of the time - A little of the time - None of the Time	No change will be done

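### The SF-36 global score is a raw 36-item sum with no missing-item rule of its own, and it includes the one-year health-transition item

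*SAP*

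**What the plan says.** **Global score.** SAP 5.7.5.1, under Quality of life, states that "a global score per patient will be derived as the sum of the individual scores at each question" and adds: "It will range from 0 to 3600".

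**Item coding.** SAP section 7 says that "each question will be coded from 0 to 100, using the table below". Dimension scores are then means of the responses, "with higher score defining a more favourable health".

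**Missing items.** The same paragraph of section 7 gives the only SF-36 rule: "Missing data will not be taken into account and will not be replaced". Section 5.7.5.1 gives no rule for the global score, and Appendix A1 contains no code.

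**Health transition.** Section 5.7.5.1 counts it among the scales: "The SF-36 consists of 36 questions divided in 9 scaled scores: General health, Reported health transition, Physical functioning". Section 7 instead lists eight dimensions "and one additional question on Reported health transition", and Protocol 10.1 names eight scaled scores without it. Its lowest code in section 7 is in the row "Fifth modality: Poor / Much worse now than one year ago / Extremely / Definitely false", so its reference point is one year before the visit.

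**Display.** SAP 5.7.5.2 plans histograms of mean global scores by treatment group and visit, but describes those graphs as also showing, or being split by, dimension.

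**The concern.** A mean of answered items and a sum of answered items react differently to a blank. The mean drops the blank from numerator and denominator. The sum keeps an implied denominator of 36 and credits the blank with nothing. Because items are coded with 0 as the unfavourable end, that is a systematic shift in one direction. A blank after dosing looks like deterioration, and a blank at baseline makes later visits look like improvement. With about six subjects per arm, one incomplete form can visibly move an arm mean.

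The transition item is a separate problem. The declared endpoint in SAP 5.7.5.1 is change from baseline, while this item asks about change over the past year. At week 12 its reference point lies about 52 − 12 = 40 weeks before dosing, and at week 6 about 52 − 6 = 46 weeks before.

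**Working it through.** **1. Reproduce the stated range.** The maximum is the number of items × 100.
- Items in the section 7 coding table: 6 + 10 + 7 + 5 + 5 + 3 = 36.
- Items in the section 7 dimension table: 10 + 2 + 4 + 3 + 5 + 4 + 2 + 5 + 1 = 36.
- 36 × 100 = 3600, which matches. Without health transition, 35 × 100 = 3500, which does not match. The transition item is therefore in the total.

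**2. Apply the section 7 rule to the sum.** With k items skipped and a uniform item score m, the total is (36 − k) × m. The proportional loss is k/36, whatever m is.
- k = 1: 1/36 = 2.8%.
- k = 10 (the physical functioning block): 10/36 = 27.8%.

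The documents give no SF-36 values, so m = 70 is an assumption, with 50 to 90 as the range. The arm-mean shift is the subject's loss divided by 6, the arm size in SAP 2.3.

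| Items skipped | Total at m = 70 (50 to 90) | Loss | Shift in a six-subject arm mean |
|---|---|---|---|
| 0 | 2520 (1800 to 3240) | 0 | 0 |
| 1 | 2450 (1750 to 3150) | 70 (50 to 90) | 11.7 (8.3 to 15.0) |
| 10 | 1820 (1300 to 2340) | 700 (500 to 900) | 116.7 (83.3 to 150.0) |

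Equivalence with the worst answer: 35 × 70 with one item blank = 2450, and 35 × 70 + 0 for one worst answer = 2450.

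The ceilings are 100 points for one item and 1000 points for ten. They are reached only if every skipped item would have been answered at 100.

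**3. Apply the other possible reading.** If any blank makes the total missing, nothing is scored as worst, but one incomplete form removes 1/6 = 16.7% of the arm at that visit.

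**4. Weight of the transition item.** It can contribute at most 100/3600 = 2.8% of the range. A move from about the same (50) to much better (100) adds 50 points, or 50/3600 = 1.4%.

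**5. Check the alternative.** The mean of answered items over the 35 non-transition items at m = 70 is (35 × 70)/35 = 70 when complete, (34 × 70)/34 = 70 with one skipped, and (25 × 70)/25 = 70 with ten skipped. The built-in drop disappears.

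**The case against.** **The missing-item rule may not govern the total.** It sits in the paragraph on dimension means. A reader might infer that the SAP scores every skipped item as worst health, but the documents do not say so; it is the arithmetic result of extending that rule to a sum. This objection stands as a limit on the claim. It does not remove the problem: SAP 5.7.1.2 says that missing-data handling is given in each relevant section, and the section defining the global score gives none. Two programmers could derive different totals from the same form.

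**The displayed comparison may be unaffected.** A reader might infer that the plotted arm differences are distorted. A single 0 to 3600 total has no dimensions, yet SAP 5.7.5.2 describes the global-score graphs as involving dimensions. What is plotted may be the dimension means, which do not have this fault. The text does not settle it, so distortion of a displayed comparison is not established.

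**Item non-response is visible and may be rare.** SAP 5.7.5.2 plans a listing of individual responses and tables by question. SAP 5.1.2 shows numbers of observations and missing data, and the protocol provides for queries on missing data. No non-response rate is given, so the frequency of the problem cannot be sized. All of this holds, but it lets a reader detect the problem without correcting the total.

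**Health transition already has its own score.** This is true, and it is only 1 item of 36. Its presence in the total is still at odds with section 7, which sets it outside the eight dimensions.

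**Conclusion.** The point holds as a minor one. The global score is defined as a 36-item sum, no missing-item rule is written for it, and both available readings are unsatisfactory. One takes 2.8% of the total per skipped item at a uniform item score (27.8% for the physical functioning block). The other loses the subject from an arm of about six. That the transition item is included is certain from the 3600 maximum.

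The percentages assume a uniform item score, and the point values assume a mean item score of 50 to 90. The 100- and 1000-point figures are ceilings, not expected losses. The score is an added summary for an exploratory objective and is analysed descriptively without tests. No primary or secondary conclusion rests on it.

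**What to change.** In SAP 5.7.5.1 and section 7:

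- Define the global score as the mean of answered items, range 0 to 100, over the 35 items excluding health transition.
- State the minimum number of answered items below which the score is missing. The documents give no basis for a figure, so the sponsor should choose and justify one. It matters because a mean can still shift when the blanks are concentrated in one block.
- Keep health transition as its own separately reported item, and make the scale count agree between section 5.7.5.1 (nine) and section 7 (eight plus one).
- In SAP 5.7.5.2, say whether the plotted global scores are this overall score or the dimension scores.

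Averaging the eight dimension scores would also remove the raw-sum drop, but it changes the weights: physical functioning would count for 1/8 = 12.5% instead of 10/35 = 28.6%. The choice should be explicit.

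The cost is about one line for the score definition plus short clarifications, made before database lock, when the SAP is due to be final. No new data are needed, and the stated range changes from 0 to 3600 to 0 to 100.
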